### **9.1 STUDY DESIGN**

Data extraction from both databases (I and II, see [section 9.4](#)) will be conducted by

. All patients will be required to have a prescription for ICS/LABA therapy [e.g. Advair (Diskus and HFA), Airduo, Breo, Dulera, or Symbicort]. The date of the first prescription of ICS/LABA within the study period (Jan 1st 2016 to Nov 30th 2018) will be defined as ICS/LABA-initiation (ICS/LABAi) date. This baseline cohort will then be followed to identify two cohorts (two arms of the study). One cohort that receives a prescription for Tiotropium Respimat® 1.25 mcg (on top of baseline ICS/LABA) will be classified as the ‘Tio’ group, and the second cohort that receives a “step-up” from baseline low-dose ICS/LABA to medium/high dose ICS/LABA or from baseline medium dose ICS/LABA to high dose ICS/LABA or an additional prescription/refill of high-dose-ICS/LABA following the first prescription of baseline high dose ICS/LABA within the study period, will be classified as the ‘NonTio’ group. The date of the first prescription for Tiotropium Respimat® 1.25 mcg in the ‘Tio’ group will be defined as the index date for the ‘Tio’ group. Similarly the date of the first prescription for a “step-up” from baseline low-dose ICS/LABA to medium/high dose ICS/LABA or from baseline medium dose ICS/LABA to high dose ICS/LABA or an additional prescription/refill of high-dose-ICS/LABA following the first prescription of baseline high dose ICS/LABA (evidenced by at least 90-days of prescription utilization) within the study period will be defined as the index date for the ‘NonTio’ group.

Patients will be required to have a minimum follow-up period of 30 days after the index date for the analyses of the primary endpoint with no limit on the maximum period (this 30-day minimum follow-up period requirement will be waived in a sensitivity analysis). Subject to sample size requirements, patients will be required to have available records for at least 12 months prior to the index date to ensure no prior use of Tiotropium Respimat® and to establish baseline patient characteristics. This 12-month period prior to the index date will be defined as the pre-index period.

Figure 9.1.1 Study Design

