## **9.5 STUDY SIZE**

The expected number of asthma patients aged 12 years and above, without concurrent COPD, and continuous enrollment for 12 months prior to the Tiotropium Respimat® date is estimated to be approximately 2,100 to be matched to double (4200 patients) the number of NonTio patients resulting in a total N =6,300. Power calculation was conducted for the primary endpoint, time-to-first exacerbation by the end of the follow-up time. The calculation was based on detecting a significant treatment effect using Cox proportional hazard model. Estimates were obtained from the MEZZO trial comparing tiotropium 2.5 µg vs. salmeterol ([P15-01655](#)). Assuming 6.4% of patients in the control group followed

up for 5.5 months will have an exacerbation (based on the salmeterol group in the MEZZO study) and assuming a constant hazard rate, equating to an exponential rate parameter of 0.012 per month for the control group and 0.0096 per month for the Tio group, the power is calculated to be 77%. Using the Primo study, assuming 26.9% of patients in the control group followed up for 11 months will have an exacerbation (based on the Tio R 5 group in the 48-week study Primo) and assuming a constant hazard rate, equates to an exponential rate parameter of 0.028 per month in the control group and 0.0224 per month in the Tio group, the power is 98%. The Mezzo-derived power calculation likely underestimates the power since our study design includes sicker patients that required a step-up in ICS treatment (not required in the Mezzo Study). While we expect that the actual power will lie between the two estimates (assuming that the patient population is similar to the less severe Primo patients and the more severe MEZZO patients), the estimated power is greater than 77%.

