## 9.11 SUBJECTS

1. Patients with least one asthma diagnosis in the inpatient setting or at least two separate instances of asthma diagnosis (separated by at least 30 days) recorded in the outpatient or emergency room setting will be included (ICD 9 CM: 493.xx or ICD 10: J45-J45.999).
2. Patients will be required to be already on ICS/LABA.
3. Patients below the age of 6 years on the ICS/LABAI date will be excluded.
4. Patients will be required to have available records 12 months prior to the index date (6 months will be used if patient exclusions due to this criteria adversely affect the study sample size).
5. Patients with a diagnosis of COPD at any time during the study period will be excluded.
6. Those who are on biologics at baseline will be removed.
7. After the PSM process, unmatched patients will be excluded.

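### The COPD exclusion in section 9.11 uses codes recorded after the index date, which could bias the Tio versus NonTio hazard ratio by an unknown amount in either direction

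*Combined protocol and SAP*

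**What the plan says.** Section 9.11, item 5, reads: "Patients with a diagnosis of COPD at any time during the study period will be excluded". Section 9.1 defines the study period by fixed calendar dates, 1 January 2016 to 30 November 2018. The index date comes later than the first ICS/LABA prescription in that period: it is the first Tiotropium Respimat prescription for Tio, and the qualifying step-up or high-dose refill for NonTio. Follow-up lasts at least 30 days "with no limit on the maximum period".

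Section 9.1 also sets a baseline window: "This 12-month period prior to the index date will be defined as the pre-index period". Item 5 does not use it. The next criterion in the list is tied to baseline: "Those who are on biologics at baseline will be removed". Section 9.12 says that ICS changes after index will not be a reason to exclude patients, because they reflect outcomes. Section 9.5 counts patients "without concurrent COPD" and gives no window for that term.

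The protocol gives no reason for the any-time window. The sensitivity analysis described in section 9.1 waives the 30-day follow-up minimum. None is planned for the COPD rule, and section 9.9 does not list the rule as a limitation.

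**The concern.** A cohort comparison that starts at the index date should decide who is in the cohort from information available by that date. Item 5 also uses the future. A patient can enter, have a first exacerbation, receive a COPD code later, and then be deleted together with the event. The longer the observation after index, the more chance there is of such a code.

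If patients who worsen are investigated more and coded more often, the deleted patients carry more than average risk. If that happens at different rates in Tio and NonTio, the retained groups no longer compare like with like on the primary endpoint, time to first exacerbation. Table 1 matches on variables recorded at or before index, so it cannot fully correct a selection that takes place afterwards.

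**Working it through.** **1. Windows side by side.**
- COPD exclusion (9.11, item 5): 1 January 2016 to 30 November 2018, the same calendar dates for everyone.
- Pre-index period (9.1): the 12 months before each patient's own index date.
- Follow-up (9.1): from index, no upper limit.
- Data extraction for Database I (9.4): from January 2015.

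The exclusion window overlaps follow-up for every patient, so codes after index count. At the other end it starts on 1 January 2016, whereas the pre-index period of a patient indexed during 2016 reaches back into 2015. A patient whose only COPD code falls in the 2015 part is not excluded on the literal wording, although the code is in the baseline window. The rule is thus too wide after index and, for early index dates, too narrow before it.

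**2. When this biases the hazard ratio.** Let q_T and q_C be the shares of Tio and NonTio patients removed only because of a post-index code, and let r be their exacerbation hazard relative to those retained, taken as equal in both groups. A group's mean hazard before removal is its retained hazard times 1 + q(r − 1). Hence, approximately:

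HR among retained = HR among all × [1 + q_C(r − 1)] / [1 + q_T(r − 1)]

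The multiplier is 1.00 if q_T = q_C or if r = 1. Bias needs both unequal removal and a link with risk.

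**3. Illustration.** The protocol gives neither q nor r. These values are assumptions:
- q_T 3%, q_C 1%, r = 2: 1.01 / 1.03 = 0.98.
- q_T 6%, q_C 2%, r = 3: 1.04 / 1.12 = 0.93. A true 1.00 would read 0.93, and a true 0.80 would read 0.74.
- q_T 2%, q_C 4%, r = 3: 1.08 / 1.04 = 1.04.

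A second parametrisation sets the removed patients' hazard at m times the group mean, so the retained hazard is proportional to (1 − qm)/(1 − q). With 5% of Tio and 2% of NonTio removed it gives 0.97 at m = 2 and 0.93 at m = 3. Larger assumed removal gives larger bias (10% versus 2% at m = 3 gives 0.81), but nothing in the protocol supports so high a figure.

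**4. Against the planned effect and precision.** Section 9.5 implies a hazard ratio of 0.0096 / 0.012 = 0.80, with log −0.223.
- log 0.93 (unrounded 0.929) = −0.074, about one third of the planned effect.
- log 0.98 (unrounded 0.981) = −0.020, about 9%.
- log 1.04 (unrounded 1.038) = +0.038, about 17% in the other direction.

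With 2,100 and 4,200 patients and the section 9.5 rates, expected events are about 376 (0.012 per month, 5.5 months) or 1,572 (0.028 per month, 11 months). The standard error of the log hazard ratio, 1/√(events × 1/3 × 2/3), is then about 0.11 or 0.05. The 0.93 case is about 0.7 to 1.4 standard errors; the 0.98 case is well below one.

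**The case against.** The strongest defence is diagnostic. COPD is chronic, and a code recorded after index may reveal disease already present but labelled asthma at baseline. The target is asthma without COPD, and section 9.9 names misclassification as a threat. If the later-coded patients had COPD all along, removing them gives the right population, and the multipliers above treat the wrong one as truth. This stands as a reason to keep the any-time rule as a sensitivity analysis. It does not make that rule safe as the only analysis, because the rule still conditions on follow-up.

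Matching also does more than nothing. If item 5 is applied before matching, as the order of the list suggests, the remaining patients are matched on control status, OCS use, admissions, ER visits and comorbidity, which rebalances whatever those variables explain. So q must be read as removal among otherwise comparable patients, and r as excess hazard beyond the matched covariates. Values of 2 to 3 on that scale are unsupported by the protocol.

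The contrasts with other text are limited. Biologic use is a treatment that can start after index, whereas COPD persists, so the baseline anchor in item 6 does not by itself prove item 5 wrong. A reader might take section 9.5 to contradict item 5, but "without concurrent COPD" sets no window and is compatible with either reading.

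A reader might also infer from section 9.12, which expects Tio patients to be more severe during follow-up too, that the rule strips high-risk patients mainly from Tio and so favours tiotropium. That expectation describes the groups in aggregate, absent a method of control. It makes unequal removal plausible but does not show it among matched patients.

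**Conclusion.** Item 5 selects on post-index information, and its literal window misses some 2015 baseline codes; both follow from the wording. Whether the hazard ratio is biased is conditional: post-index COPD coding must differ between Tio and NonTio and must be linked to exacerbation risk beyond the matched covariates. The protocol shows neither and gives no rates, so size and direction are unknown. The illustrative multipliers run from about 0.93 to 1.04 and rest wholly on assumed removal of 1% to 6% and 2 to 3 times the hazard. The stronger statement, that high-risk patients are in fact removed unevenly, is not supported. The change is still worth making, because the exposure to bias is avoidable, no planned analysis would reveal it, and the upper end of the illustration is not negligible beside a planned hazard ratio of 0.80.

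**What to change.** Reword item 5 so that, for the primary analysis, patients are excluded for a COPD diagnosis recorded in the pre-index period up to and including the index date. This also captures the 2015 codes for patients indexed in 2016. If the 6-month fallback in item 4 is used, state the COPD window that then applies.

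Keep the any-time exclusion as a named sensitivity analysis, with matching repeated after the exclusion, on the ground that a later code may reveal COPD already present. Report the number and share of patients with a first COPD code after index, by group. That table replaces the assumed q values with observed ones and shows whether the choice of window matters.

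The cost is one line of wording, one further matched analysis and one table, with no new data. The downside is that some patients with COPD unrecognised at baseline stay in the primary set; the sensitivity analysis shows how much the result depends on them.

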### 9.11.1 Cases

NA

### 9.11.2 Controls

NA

## 9.12 BIAS

### Channeling Bias Mitigation

Introduction of channeling bias in this study is highly likely using retrospective claims data based on asthma medication use; patients between the two cohorts may differ in baseline control and severity levels. On aggregate, patients for whom Tiotropium Respimat® 1.25 mcg was added (vs NonTio) are likely to be less well-controlled and more severe both at baseline and during the follow up period. Absent a method to control for this channeling bias, it is likely that placing sicker patients in the Tiotropium Respimat® 1.25mcg group will confound an accurate comparison of cost, resource use, and other outcomes between the groups. Two design features of our study will help mitigate this bias. First, our comparison (NonTio) group will be required to step-up their baseline ICS/LABA dose or have an additional prescription/refill of high-dose-ICS/LABA following the first prescription of baseline high dose ICS/LABA within the study period. Second, we will use Propensity Score Matching (PSM) to match patients on key measures of disease control and severity as listed in [Table 1](#), such as demographics, Charlson Comorbidity Index (CCI) score, specific comorbidities, number of prescriptions (overall and asthma-related medications). This baseline matching strategy will be particularly important to ensure that patients in the TIO group who have a corresponding increase in their ICS dose at or prior to the date of their TIO prescription (for example, if the patient has an exacerbation), will be matched to a corresponding NonTIO patient in terms of increased ICS dose or additional ICS prescription. It should be noted that after the prescription index date for both Tio and NonTio patients, we anticipate changes in ICS medication for patients in both cohorts. These ICS medication changes reflect patient

outcomes in the follow-up period, where patients who encounter exacerbation in either group are likely to see a change in the ICS dose.

As a result, post-index period ICS medication changes will not alter the classification of patient groups nor will it be the basis for exclusion of these patients.

We will conduct 1:2 matching using a nearest neighbour matching approach with a radius of  $0.2 * SD(\log(P))$ . This will be conducted in both databases (IMS: Cohort I and EMRClaims+: Cohort II) separately.

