**Table 1: Matching Parameters**

Variable Name and Type	Description	Applicable to Study Cohort: 1=IMS, 2=EMRClaims+
ICS/LABA dose on ICS/LABAI date	The dose level of the first prescription on the ICS/LABAI date (low, medium, or high)	1 and 2
Demographics (categorical and continuous variables)	Age (10-year increments) and Gender Male/Female), Region (if available, Northeast, Midwest, South, West)	1 and 2
CCI (continuous variable)	Charlson Comorbidity Index score	1 and 2
Specific comorbidities (categorical variables)	Cardiovascular conditions, cerebrovascular diseases, hypertension, diabetes, metabolic and endocrine comorbidities, anxiety and depression, gastro-esophageal reflux disease, cancer and obesity identified using appropriate ICD codes. All above measures will be coded as binary (yes/no) variables.	1 and 2
Medications (categorical variable)	Polypharmacy level matched within a range of 2 drugs (for example, 0-2,3-5,6-8,8-10 and so on).	1 and 2
Asthma Control Status: Well Control or Poor Control (categorical variable)	‘Well Controlled’ if patient has no prescriptions for an OCS, and no asthma-related emergency department visits or hospitalizations other than the first diagnosis recorded in the data extracted (Ref: Stempel JACI 2005). Categories will include Well Controlled and Not Well Controlled.	1 and 2
Hospital admissions Outpatient visits ER visits and OCS use (categorical variables)	Poorly Controlled patients (“Not Well Controlled”) will further be matched based on the presence of asthma-related admissions, outpatient visits, and ER visits or use of OCS during the pre-index period.	1 and 2
Eosinophil levels (EMRClaims+ database only) (categorical variables)	Eosinophil level categories: <150 cells/μL, 151-300cells/μL, 301-400 cells/μL, ≥400 cells/μL (as available)	2
Asthma Control Test (ACT) results (EMRClaims+ database only) (categorical variables)	ACT score categories developed based on data distribution (as available)	2

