## **9.7 DATA ANALYSIS**

### **9.7.1 Main analysis**

We will provide the sample attrition at each step of the inclusion-exclusion criteria as well as a baseline demographic and comorbidity breakdown. We will provide a comparative breakdown in baseline measures for the unmatched and matched cohorts to assess if PSM eliminated baseline differences. For the primary endpoints analysis, we will calculate the time to first exacerbation per patient and compare it between the two groups (Tio vs. NonTio). For secondary endpoint analyses we will compare the rate of exacerbation, proportion of patients with exacerbations after 6 months and one year (based on Kaplan Meier estimates), HCRU and average cost during follow-up and compare them between the two groups (Tio vs. NonTio).

The primary outcome of the study will be analyzed using Cox proportional hazard modelling. The secondary outcome of rate of exacerbation per patient will be analyzed using negative binomial regression. This technique works on the assumption that the rate of exacerbation varies among every subject in the study ([P16-06846](#)). Also this model accounts for overdispersion of data which is likely to happen due to variability between the patients. Balance in covariates will be checked after matching. If PSM was able to balance all observed baseline characteristics, the regression models for outcomes will be limited to the databases (IMS and EMR) and to the key independent variable of interest (namely Tio use vs. ICS/LABA dose increase) and model overfitting is not, therefore, of concern. However, if there are unbalanced baseline characteristics, we will include these characteristics in the regression as covariates. For regression model covariate selection we

will also estimate the multicollinearity of covariates by assessing their correlations of independent variables. For example, if comorbidities from the specific list are also included in CCI, they will only be included in the CCI.

In order to handle missing data, in the PSM we will create a category variable (‘missing data’) for each covariate to ensure that patients with that variable and without that variable are respectively matched. Patients with missing prescription data required for classification of the treatment groups will be excluded. Patients with missing lung function scores and ACT scores at baseline and in the follow up period will be excluded from these respective secondary analyses.

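### The propensity score has no tobacco-use variable, so the primary hazard ratio may carry residual confounding by smoking among patients without a COPD code

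*Combined protocol and SAP*

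**What the plan says.** Section 9.12 (Channeling Bias Mitigation) states: "Introduction of channeling bias in this study is highly likely using retrospective claims data based on asthma medication use". It describes the expected difference as one of asthma control and severity, and names two design features that should help. One is the requirement that NonTio patients step up their dose or refill high-dose ICS/LABA. The other is propensity score matching, to "match patients on key measures of disease control and severity as listed in" Table 1.

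The specific comorbidities in Table 1 are: "Cardiovascular conditions, cerebrovascular diseases, hypertension, diabetes, metabolic and endocrine comorbidities, anxiety and depression, gastro-esophageal reflux disease, cancer and obesity identified using appropriate ICD codes". The other rows are starting ICS/LABA dose, demographics, CCI, polypharmacy, asthma control status, and asthma-related admissions, visits and OCS use. Eosinophils and ACT score are added for EMRClaims+ only, as available. Tobacco use, allergic rhinitis, sinusitis and nasal polyps are not listed there or anywhere else.

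Section 9.11, item 5, says: "Patients with a diagnosis of COPD at any time during the study period will be excluded".

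Section 9.7.1 makes the Cox model depend on the balance check. "If PSM was able to balance all observed baseline characteristics", then "the regression models for outcomes will be limited to the databases (IMS and EMR) and to the key independent variable of interest". Otherwise the characteristics found unbalanced are added as covariates.

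**The concern.** The study compares adding a long-acting anticholinergic with more ICS/LABA, and the outcome is asthma exacerbation. Smoking could plausibly be related both to which option is prescribed and to exacerbation risk, which would make it a confounder. Excluding recorded COPD removes the patients whose obstructive disease has been coded, but a smoker without that code stays eligible.

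Matching and the regression fallback both work only on variables that have been derived. If tobacco use is not derived, it cannot appear in the balance table, cannot be found unbalanced and cannot enter the Cox model directly. The matched cohorts could be reported as balanced while still differing in smoking. The plan describes no negative control, E-value or other bias analysis that would show how much this could matter. The stake is a shifted estimate of effect for the payers and prescribers named in section 7. Any change in power follows from that shift.

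**Working it through.** **1. Is the variable absent?** The plan states no figure to reproduce here, so this step is a reading of Table 1 and sections 9.3.3, 9.7.1, 9.11 and 9.12. No tobacco, upper-airway, allergic or respiratory-infection variable is named. COPD is handled only as an exclusion. The 9.7.1 fallback is limited to observed characteristics. The omission is confirmed.

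**2. Inputs for an illustration of size**
- From section 9.5: 2,100 Tio and 4,200 NonTio (Tio fraction 1/3). Monthly hazards are 0.0096 vs 0.012 with stated power 77%, and 0.0224 vs 0.028 with stated power 98%. Both pairs give HR 0.80.
- Assumed, because the documents are silent: tobacco prevalence in each matched arm, the hazard ratio RR of tobacco use for exacerbation, and two-sided alpha 0.05.

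**3. Event counts and the plan's own power**
- Power = Φ(|ln HR| × √(D × 1/3 × 2/3) − 1.96) = Φ(|ln HR| × √(2D/9) − 1.96).
- Second scenario, 11 months: D = 2,100(1 − e^(−0.0224×11)) + 4,200(1 − e^(−0.028×11)) = 459 + 1,113 = 1,572. Power = Φ(0.2231 × 18.69 − 1.96) = Φ(2.21) = 98.7%, in line with the stated 98%.
- First scenario, 5.5 months: D = 108 + 268 = 376, which gives 53%, not 77%. The events needed for 77% are D = (1.96 + 0.739)² / (0.2231² × 2/9) ≈ 658. The 658 used below is therefore solved back from the stated 77% and does not follow from the stated follow-up.

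**4. Bias factor**
For an unmeasured binary confounder, B = [1 + p_Tio(RR − 1)] / [1 + p_NonTio(RR − 1)], and observed HR = 0.80 × B. Central case: B = (1 + 0.25 × 0.5) / (1 + 0.15 × 0.5) = 1.125 / 1.075 = 1.047, so HR = 0.837.

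| Tio / NonTio tobacco use | RR | B | Observed HR | Power, 658 events | Power, about 1,570 events |
|---|---|---|---|---|---|
| 15% / 15% | 1.5 | 1.000 | 0.80 | 77% | 99% |
| 20% / 15% | 1.5 | 1.023 | 0.82 | 68% | 96% |
| 25% / 15% | 1.5 | 1.047 | 0.84 | 57% | 91% |
| 30% / 15% | 2.0 | 1.130 | 0.90 | 23% | 47% |
| 15% / 25% | 1.5 | 0.956 | 0.76 | 90% | >99% |

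Event counts are held fixed across rows. The last row reverses the central case: the same gap the other way would flatter Tio.

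**5. How strong would a confounder have to be?** The E-value for HR 0.80 is 1.25 + √(1.25 × 0.25) = 1.81. To account for the whole of an observed 0.80, a confounder would need an association of about 1.8-fold with both treatment and outcome.

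**The case against.** A reader might infer that smoking-related channeling to tiotropium is present and will bias the hazard ratio against Tio. The documents do not support that. They never mention smoking, and section 9.12 describes channeling in terms of control and severity. Existence, size and direction all rest on assumption.

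Nor is Table 1 the plan's only defence. Section 9.12 also relies on the step-up or refill requirement. Section 9.11 excludes biologic users and anyone with a COPD diagnosis at any time in the study period, including one first coded after index. Cardiovascular and cerebrovascular disease, cancer, CCI, asthma control and prior OCS or ER use may absorb part of any smoking difference. It would therefore be too strong to say that no correction is possible. These points stand, and they limit the concern to residual confounding of unknown size.

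The covariate list is not fully closed. Section 9.3.3 introduces the comorbidities as examples, and 9.4 leaves covariates to be finalized after data evaluation. But neither names tobacco as a candidate, so neither supplies the variable. Section 9.9 warns in general terms about missing clinical history and says that no effectiveness claims should be made from the study. That tempers the consequence without closing the gap.

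For the airway and allergic comorbidities, nothing in the documents gives a mechanism or a direction. They do not carry the point.

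**Conclusion.** The concern holds in a limited form. Tobacco use is not in the propensity score, and the 9.7.1 fallback reaches only observed characteristics. The primary hazard ratio may therefore carry residual confounding by smoking among patients without a COPD code, beyond what correlated covariates absorb.

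Under the assumed central case, HR 0.80 becomes about 0.84. The cost in power depends heavily on events: about 57% remains at 658 and about 91% at about 1,570. The plan expects its power to lie between its two scenarios, so quoting only the weaker one would exaggerate the loss. The omission itself is certain. Whether it matters, by how much and in which direction cannot be settled from the documents. This is a cheap improvement worth making, not a demonstrated bias.

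**What to change.** Add a binary row for tobacco use/nicotine dependence to Table 1, identified by ICD code in the pre-index period in both databases, in the same way as obesity and reflux. Include it in the propensity model and in the post-matching balance table, so that the 9.7.1 adjustment rule covers it. Airway and allergic comorbidities (allergic rhinitis, chronic sinusitis or nasal polyps, lower respiratory infection) can be added in the same way as an optional extra. A prespecified E-value or a short bias table like the one above would address smoking that is not coded.

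The cost is a few code lists and propensity terms. Tobacco use is under-coded in claims, so control will be partial, and slightly fewer close matches may be found.

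### Matching on one propensity score does not deliver the variable-by-variable matches that the plan describes, and leaves balance within baseline ICS/LABA dose level dependent on the score model

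*Combined protocol and SAP*

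**What the plan says.** Section 9.12 (Channeling Bias Mitigation) states the whole matching procedure: "We will conduct 1:2 matching using a nearest neighbour matching approach with a radius of" 0.2 × SD(log(P)). It adds: "This will be conducted in both databases (IMS: Cohort I and EMRClaims+: Cohort II) separately". No exact or stratified step is described.

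Four other statements are worded at the level of the variable or the pair:

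- Section 9.7.1: a missing-data category is created for each covariate "to ensure that patients with that variable and without that variable are respectively matched".
- Table 1, medications: "Polypharmacy level matched within a range of 2 drugs".
- Table 1, poorly controlled patients: these "will further be matched based on the presence of asthma-related admissions, outpatient visits, and ER visits or use of OCS during the pre-index period".
- Section 9.12: a Tio patient with an ICS increase at or before the Tio prescription "will be matched to a corresponding NonTIO patient in terms of increased ICS dose or additional ICS prescription".

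Table 1 lists dose as a three-level variable taken on the ICS/LABA initiation date, and control status as two levels ("Categories will include Well Controlled and Not Well Controlled"). Section 9.7.1 plans to compare baseline measures before and after matching and to add unbalanced variables to the regression. It names no balance metric or threshold. If all variables balance, the outcome models contain only treatment and database.

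**The concern.** A programmer who follows Section 9.12 will not produce what Sections 9.7.1 and 9.12 and Table 1 describe. Two patients with nearly equal scores can have different doses, control status, drug counts or missingness, because differences on one variable offset differences on another.

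Baseline dose is the variable that matters most. Under Section 9.1, a NonTio patient who starts on low or medium dose enters by a step-up, and one who starts on high dose enters by a further prescription of the same dose. The objective in Section 8 is Tio against an ICS dose increase, so the low- and medium-dose comparison lies closest to it. Section 9.9 already concedes that including continuing high-dose users complicates interpretation. If matched sets cross dose levels, comparability inside a level depends on the score model being right, including any interaction between dose and control status. The planned check looks at variables one at a time in the whole matched cohort and would not show a failure there.

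**Working it through.** **The plan's own figures.** Sample size: 2,100 + 2 × 2,100 = 6,300, as in Section 9.5. For the Primo scenario (0.028 v 0.0224 per month, 11 months):

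- Expected events: 4,200 × (1 − e^(−0.308)) + 2,100 × (1 − e^(−0.2464)) = 1,113 + 459 = 1,572.
- Schoenfeld power at two-sided 0.05 (assumed; the plan states no alpha) = Φ(0.2231 × √(1,572 × 2/9) − 1.96) = Φ(2.21) = 98.65%, which agrees with the stated 98%.

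The MEZZO figure of 77% does not reproduce at 5.5 months (53%). That is a separate matter and nothing here rests on it.

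**How often pairs would differ.** The plan gives no dose mix, control prevalence or NonTio pool size, so all are assumptions. For orientation, random pairing of two groups with the same dose shares p differs in 1 − Σp² of pairs:

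- shares 25/45/30%: 1 − 0.0625 − 0.2025 − 0.09 = 64.5%
- shares 5/15/80%: 1 − 0.0025 − 0.0225 − 0.64 = 33.5%

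Simulated matching used a logistic score on covariates like those in Table 1, greedy 1:2 matching without replacement and the plan's caliper. It gave:

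- dose differs in 53–64% of pairs when the dose mix is spread and similar in the groups, 42–46% when high dose dominates, and 13–34% when dose strongly predicts Tio;
- control status differs in about 34–47% (32–41% in a second set of simulations with a logit caliper and larger pools; 48% at the extreme with 50 Tio patients);
- polypharmacy band differs in about 60–70%.

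**Overall balance under score-only matching.** The largest standardised difference was 0.02–0.05 with 1,900 Tio patients, 0.07–0.16 with 200 and 0.17–0.22 with 50.

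**Balance within dose level.** When the score had main effects only and the true dose-by-control interaction was omitted, poor control differed between groups by 6–16 percentage points within a dose level. The spurious baseline hazard ratio was 1.5–5%. Exact dose × control cells removed both. The sizes depend on the interaction assumed.

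The reason the marginal check can miss this is arithmetic. Take 45% of matched patients on high dose and 55% on low or medium. A 10-point excess of poor control among high-dose Tio patients is cancelled overall by a deficit of 10 × 0.45/0.55 = 8.2 points in the rest: 0.45 × 10 − 0.55 × 8.2 ≈ 0.

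**Cost of exact cells** (3 doses × 2 control states). Assumed: dose mix 15/40/45% in Tio and 25/45/30% in NonTio; poor control 60% v 45%.

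| Tio patients | NonTio per Tio in pool | Pairs, score only | Pairs, exact cells | Extra loss | Largest std. difference, before → after |
|---|---|---|---|---|---|
| 1,900 | 2 | 2,685 | 2,658 | 1.0% | 0.028 → 0.025 |
| 1,900 | 5 | 3,528 | 3,520 | 0.2% | 0.033 → 0.020 |
| 200 | 2 | 267 | 250 | 6.4% | 0.080 → 0.092 |
| 200 | 5 | 363 | 351 | 3.3% | 0.083 → 0.090 |
| 50 | 2 | 55 | 44 | 20% | 0.221 → 0.292 |
| 50 | 5 | 81 | 72 | 11% | 0.171 → 0.223 |

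Across all scenarios the extra loss with 200 Tio patients ran from 0.3% to about 6%. Losing 1% of matched sets moves Primo power from 98.65% to 98.57%; losing 5% gives 98.2%. Polypharmacy-band mismatch stays at about 55–69% of pairs after the change.

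**Size of Database II.** If Tio patients split in proportion to lives (an assumption; Sections 9.4 and 9.10 give 0.69 million against 40 or 150 million), Database II holds 2,100 × 0.69/40.69 ≈ 36 or 2,100 × 0.69/150.69 ≈ 10 of them.

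**The case against.** Propensity matching aims at group balance, not identical pairs, so discordant pairs are not evidence of bias. The planned outcome models do not use the pairs, no dose-level analysis is planned, and Section 9.7.1 provides a balance check with regression adjustment. All of this stands. It rules out the inference that a high share of dose-discordant pairs means a biased hazard ratio. What it leaves open is balance within dose level, which the check does not cover.

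A reader might also infer that about half of the pairs will differ on dose. The documents do not support that figure. They give no dose distribution, and the range runs from 13% to 64%, with the low end where dose strongly drives the choice of Tio.

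Parts of Table 1 can be read more mildly: the two-drug range as a coding band, and the further matching as a nested covariate in the score. That is fair. It does not rescue the missing-data statement in 9.7.1 or the ICS-increase statement in 9.12, which are worded as assurances about who is matched to whom.

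Finally, exact strata might be thought to repair everything at no cost. They do not. Polypharmacy, event type and missingness remain unmatched. The ICS-increase statement has no corresponding variable, since Table 1 holds dose only on the initiation date. In a small Database II the loss may be material, and with 50 Tio patients the largest standardised difference rose.

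**Conclusion.** The concern holds in a limited form. The method in Section 9.12 cannot deliver the variable-level matching that the plan describes, and the texts should be brought into line. The mismatch range above is conditional on assumed dose mixes, control prevalence, covariate effects and pool size, and is a description of the matching rather than a measure of bias. Overall balance is likely to be good in Database I.

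The substantive gap is that balance within the dose level that fixes the NonTio entry route depends on the score specification and goes unchecked. Under an omitted interaction the effect on the hazard ratio was a few per cent, so this is a worthwhile improvement rather than a fatal flaw. The low cost is established for Database I only. The unstated NonTio pool size matters more to reaching 6,300: with three NonTio patients per Tio patient, score-only matching found two controls for just 29–73% of 1,900 Tio patients.

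**What to change.** In Section 9.12:

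1. In Database I, match exactly on baseline ICS/LABA dose level and control status, then take the two nearest neighbours on the score within the caliper inside each stratum.
2. In Database II, do the same only if cell counts allow. Prespecify the fallback (fewer exact variables, or score only) and report the loss. Do not require exact strata on eosinophil or ACT missingness, which would give up to 3 × 2 × 2 × 2 = 24 cells.

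In Table 1 and Sections 9.7.1 and 9.12:

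3. Reword the polypharmacy, event-type, missing-data and ICS-increase statements as balance targets. For the last, add a pre-index dose-change variable or drop the statement.
4. State a balance metric and threshold, and apply it overall and within dose level.

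The cost is a small change to the matching code and some wording, about 0–1% of matched pairs in Database I, and possibly over 10% in Database II with about 50 Tio patients (fewer were not simulated). The mixture of step-up and continued high-dose patients acknowledged in Section 9.9 remains.
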